Within the last couple of years, a rising interest is seen in expression and storage of breastmilk before birth (antenatal breastmilk expression = aBME), to ensure an exclusive mother's milk diet and enhance the process of lactogenesis. It has been a general concern that aBME, could induce preterm labor due to rising oxytocin levels. This does not seem to be the case: In a recent published randomized controlled trial by Forster et al (12), 635 pregnant women with diabetes were randomized to either start aBME from week 36 of pregnancy or standard care (no aBME). During the first aBME they were monitored with cardiotocography surveillance, and some women had increased uterine activity, but no episodes of tachysystole, hyperstimulation or preterm birth. These findings were evaluated by a safety committee and was not found to be a risk factor for the fetus or for preterm birth. The authors found no difference between the groups in the proportion of infants admitted to the NICU or gestational age at birth. Furthermore, they found no difference between the groups in birth characteristics (eg. Onset of labor, type of birth or blood loss). They conclude that their study indicates that it is safe to advise low risk pregnant diabetic women to express breastmilk from gestational age 36. In addition, a systematic review of breastfeeding (of siblings) during pregnancy, found comparable rates of preterm birth between breastfeeding pregnant women and non-breastfeeding pregnant women (13). Furthermore a randomized study from 2015 comprising 200 pregnant women found that starting aBME at term, shortened the time from initiation to full establishment of breastfeeding (14). Recently, Foudil-Bey et al. did a scoping review to evaluate aBME outcomes (15). They identified twenty articles eligible for the review. The initiation time of aBME differs among the included studies, with twelve of the studies expressing BM after week 36. Four studies recommend to start expressing BM between 32 and 36 weeks of gestation, two before week 32 and the remaining two studies did not specify the timing of aBME. The studies who recommend to start aBME before week 36 were old and weak in methodology. They conclude, that existing studies on aBME varies widely in objectives, target population, interventions and outcomes, and that higher quality studies with clear hypothesis and populations are needed to determine safety and efficacy of aBME.

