In a pilot randomized study, we will include 60 healthy pregnant women. We will allocate 30 women to start aBME from week 34+0 of pregnancy until delivery and compare them to 30 women who does not perform aBME. All women included in this study will receive standard care, and have an individual consultation with a breastfeeding trained midwife in week 33 of their pregnancy. The women allocated to the intervention group will besides breastfeeding consultancy, also be taught how to perform aBME and store breastmilk correctly during the midwife consultation. To detect any signs of uterine contractions or fetal influence a cardiotocography (CTG) will be performed in the intervention group before, during and after the first aBME. In total 40 minutes of CTG surveillance. If the CTG is unclear, it will be assessed by the obstetric doctor in charge of this study, [name] or a substitute. In case of pathological CTG, the women will be send to the obstetric emergency department for further assessment. If the CTG is normal the women in the intervention group can perform aBME 5 minutes from each breast two times per day from week 34 until birth, and collect and store any expressed milk. They will be provided with a schedule to register their aBME sessions (Please see attachment).

Participants will receive both written and oral information about the trial and the intervention group will in addition receive safe storage of MOM (please see attachment 1, 2) and be provided with the needed syringes and labels for expressed milk. Participants will be instructed to be aware of precautions

related to aBME such as: continuous excessive painful contractions, vaginal bleeding or decreased fetal movements. In case of such symptoms they have to contact obstetric emergency department. During the intervention and 8 weeks after birth the participating women will receive weekly push-messages through an application on their smartphone. The messages include short questions about the aBME as well as regarding feeding of the infant after birth. At the end of the study we want to evaluate the mothers experience with the study through an online questionnaire. The questionnaire will be submitted as a supplement to this protocol when finished. All data is managed through OPEN/REDCap and stored in a secure server ([OPEN - Open Patient data Explorative Network - forside \(rsyd.dk\)](http://OPEN - Open Patient data Explorative Network - forside (rsyd.dk)))

Trial design

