
• Age• Smoking• Medications• Prepregnancy BMI• Delivery mode	
• Gestational age at birth• Gender• Anthropometry at birth• APGAR scores at 1 and 5 min• Umbilical cord pH• Feeding mode if hospitalized

Figure 1: Overall study design

Time	28-32 weeks of pregnancy	33 weeks	34 weeks	36 weeks	37 weeks	Admission for birth	8 weeks post partum
ENROLLMENT							
Eligibility for study screen	✗						
Informed content and information on email	✗						
Randomization to either active aBME or no aBME	✗						
INTERVENTION							
Group A: Midwife consultation		✗					
Group A: aBME 10 min a day intervention group A			→				
Group B: Midwife consultation		✗					
Group B: no aBME			→				
DATA COLLECTION							
Demographic maternal data	✗						
							✗

Obstetric data from medical records								Figure 2:
Neonatal data from medical records	Enrollment	Post randomization (intervention?)			Post-partum			Detailed
aBME data, and infant feeding data (App-tracking)								schedule
Mother's experience with the intervention (questionnaire)								of

participant enrolment, intervention and data assessment

Figure 3: Gantt diagram of project main time schedule

Event	Time	2021		2022			2023			2024		
Protocol writing and approval												
Ethical approval												
Training of staff and recruitment video production												
Patient recruitment and randomization												
August. 2022 – August. 2023												
Intervention												
August 2022 – August. 2023												
Data collection and outcome analyze												
Article writing												
Publication												

Outcomes:

Primary outcome:

1. Gestational age at birth comparing the two groups

Secondary outcomes

1. number of weekly antenatal stimulations/expressions (aBME) before birth
2. number of women in intervention group capable of expressing any milk
3. breastfeeding rates 1, 2, 4, 6 and 8 weeks after birth comparing the two groups
4. number of exclusively breastfeeding versus partial breastfeeding in each group at 1, 2, 4, 6 and 8 weeks after birth

5. Contractions and/or fetal stimulation during aBME, assessed with CTG
6. Women's experience with the intervention (separate qualitative study)

Sample Size

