## 4. Analysis

### 4.1 Baseline characteristics

We will check the distribution for all reported data. The distribution will be checked by QQ plots and histograms. The normally distributed data will be reported as mean and standard deviations (SD) and the non-normally distributed data will be reported as median and interquartile ranges (IQR). Categorical data will be reported as numbers (n) and percentages (%).

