#### Breastfeeding consultation

- Received other breastfeeding counseling (yes/no)
- Breastfed as a child (yes/partially/no)
- Partner participating in breastfeeding consultation (yes/no)

Only intervention group:

- CTG before stimulation (normal, deviant, or pathological)
- CTG under stimulation (normal, deviant, or pathological)
- CTG after stimulation (normal, deviant, or pathological)

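### Protocol secondary outcome 5 asks for contractions on CTG, but the SAP's only CTG variable is an undefined three-level grade that does not record them

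*Protocol*

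**What the plan says.** **Protocol.** Item 5 of the secondary outcomes reads "Contractions and/or fetal stimulation during aBME, assessed with CTG". The Intervention section gives the purpose of the recording: "To detect any signs of uterine contractions or fetal influence". It also says who is recorded and when: a "cardiotocography (CTG) will be performed in the intervention group before, during and after the first aBME". The length is given as "In total 40 minutes of CTG surveillance", with no split between the three segments. The planned number of women with a trace follows from "We will allocate 30 women to start aBME from week 34+0 of pregnancy until delivery".

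**SAP.** Section 4.1, under Breastfeeding consultation, lists CTG for the intervention group at three time points. The middle entry is "CTG under stimulation (normal, deviant, or pathological"), and the other two use the same three levels. Neither document defines the levels. The opening of section 4.1 sets the reporting rule: "Categorical data will be reported as numbers (n) and percentages". Sections 4.2.1 and 4.2.2 cover gestational age, self-reported adverse events, breastfeeding, and the frequency and volume of expression. CTG is not among them.

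**The concern.** The outcome asks whether contractions occurred; the planned variable asks how the trace was graded. The protocol's Background shows why these can differ. In the earlier randomised trial of expression from week 36, "some women had increased uterine activity, but no episodes of tachysystole, hyperstimulation or preterm birth", and a safety committee did not regard the findings as a risk. Traces of that kind might receive the most favourable grade. A full set of such grades could then mean no contractions or many, and a less favourable grade would not show whether the reason was uterine or fetal.

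The possibility that expression provokes labour is the safety concern named in the Background, and contractions are among the grounds for stopping listed under Interruption of the trial. The pilot is meant to inform a larger trial and possibly work at earlier gestations. It would collect up to 30 recordings made during expression and report nothing from them on contractions.

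**Working it through.** The plan states no figure for this outcome, so there is none to reproduce. The check is first of text, then of what a contraction variable could deliver.

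**Outcome against variable**

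| Part of outcome 5 | SAP variable from CTG | Answered? |
|---|---|---|
| Contractions | None for presence, number or frequency | No |
| Fetal response | Three-level grade per time point, levels undefined | Possibly in part |

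**Other contraction data**

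- SAP 4.2.1 lists regular contractions and Braxton Hicks contractions as adverse events. They are self-reported and collected in the intervention group only.
- Protocol, Data collection, takes preterm contractions from medical records after birth. These are not tied to an expression session, and the SAP lists no variable for them.

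Neither source is a reading taken while the woman expresses.

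**What a yes/no item could show**

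Inputs: n = 30 at most (Protocol, Intervention); n = 24 as an assumed 20% loss (30 × 0.8). The interval is exact (Clopper-Pearson): lower limit is the 0.025 quantile of Beta(x, n − x + 1), upper limit the 0.975 quantile of Beta(x + 1, n − x). For x = 0 the upper limit reduces to 1 − 0.025^(1/n).

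- 0/30: 1 − 0.025^(1/30) = 0.116, so 0 to 11.6%
- 1/30: 0.1 to 17.2%
- 3/30: 2.1 to 26.5%
- 6/30: 7.7 to 38.6%
- 0/24: 1 − 0.025^(1/24) = 0.142, so 0 to 14.2%

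The chance of seeing at least one woman with contractions is 1 − (1 − p)^30. The documents give no rate, so p is assumed:

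- p = 2%: 45%
- p = 5%: 79%
- p = 10%: 96%

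**What a paired test could show**

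In an exact McNemar test with k women changing, all in one direction, the two-sided p-value is 2 × 0.5^k. Five changes give 0.0625 and six give 0.031. At least six one-way changes would be needed to pass 0.05, so estimation suits this outcome better than a test.

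**The case against.** The strongest reply is that the SAP does plan something. The grades fall under the n-and-percentage rule, so a table across the three time points would be produced, and for a one-arm pilot item a descriptive table is a reasonable form. This stands. A reader might infer that CTG is not analysed at all, but the documents do not support that. What is missing is the contraction variable.

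A reader might also take the place in section 4.1, Baseline characteristics, as a demotion. It shows little, because that section also lists gestational age at birth and breastfeeding rates. The relevant difference is that those items return in 4.2 and CTG does not.

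It is tempting to say that the grade rates the trace as a whole and would hide contractions. The documents do not say so. The levels are undefined, each segment has its own grade, and contractions may or may not influence it. All that can be said is that the grade alone does not state whether they occurred.

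Finally, the absence from 4.2.2 could be a loss of text. The items there run d, e, a, b with no c, and the section numbers jump from 4.2 to 4.5. No gap is visible at that point in the supplied text, but the original should be checked. Even if an item c on CTG exists, the variable listed in 4.1 is still a grade.

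**Conclusion.** The point holds for the contraction half of outcome 5: as the SAP stands, CTG cannot answer it. The fetal half may be partly served by the grades. This rests on the SAP text as supplied, subject to the check for item c.

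Three stronger inferences should be avoided:

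- The 11.6% limit is not the cost of the omission. It is a limit of a sample of 30 and remains after the fix; what the omission costs is the ability to state any rate or limit.
- CTG is not the only contraction information, given the medical records and the self-reports. It is the only instrument reading during expression.
- Nothing shows a within-woman comparison to be the most sensitive safety test available. CTG covers one session, whereas SAP 2.2 refers to fourteen a week, and there is no control recording to separate response from spontaneous activity.

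The gap affects a secondary safety outcome, not the primary analysis. It is worth correcting because the traces are already being made.

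**What to change.** 1. Check the original SAP for item c in 4.2.2.
2. For each of the three segments of the existing 40-minute trace, record whether contractions are present (yes/no), with a count where readable. Rates per 10 minutes are not needed to answer the outcome, and the segment lengths are not given.
3. List outcome 5 in SAP 4.2.2. Report the number and proportion of women with new contractions, meaning none before stimulation and some during or after it, with an exact 95% confidence interval. State how many traces were readable and how many women already had contractions beforehand.
4. Describe the within-woman change across the segments without testing it.
5. Keep the grade, and state what each level means and which part of the outcome it serves.

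The cost is one extra item per trace and one table; no new procedure is required. The result will still be imprecise, limited to the first session and without a control recording. SAP 3.5 dates the start of recruitment to August 31, 2022, and neither document says that traces are stored, so women already enrolled can be included only if their traces were kept.

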2. BMI <27
3. Danish speaking
4. Singleton pregnancies
5. Planning to exclusively breastfeed their infants and deliver at Odense University Hospital (Odense and Svendborg)

Exclusion:

1. Suspected fetal intrauterine growth restriction or known major fetal anomaly
2. Women at risk of preterm birth with one of the following diagnoses: Placenta previa, premature preterm rupture of membranes (PPROM) or previous cervical conization
3. Women taking medications where breastfeeding is contraindicated
4. Women with prior breast surgery: Breast reductive surgery or breast implants

Ethical approval

Application for the Ethical Committee of Southern Denmark (project number: 86409) is done and the committee decided that no regional ethical approval is necessary in order to perform this study. The Research Ethics Committee of University of Southern Denmark has approved the study (Project ID: RECID281). All data collected will be entered and stored on a secure server in the Region of Southern Denmark, OPEN (www.open.rsyd.dk) and the project is approved by the Data Protection Agency at the Region of Southern Denmark. The study will be registered at clinicaltrials.gov.

Recruitment and information

[figure not shown]
Participants will be recruited using video and text announcing on social media and in outpatient/midwife clinics in the department of obstetrics. If the women are interested in participation, they click on a link and fill in an online document with contact information (telephone and email) and confirm that they comply with the inclusion criteria. After conforming their interest in participating, they receive written information about the trial (Appendix 1) through email. Following, primary investigator or others in the study group will contact them by telephone within 2-4 days to give oral information. Signed written consent will be obtained using E-Boks. Then randomization can be done and consultation in week 33 can be planned by the project-midwife by telephone.

Randomization

When the women have given informed written consent, they will be randomized to either group A (intervention) or B (control). Randomization will be done using a web-based randomization program (REDCap in OPEN). Baseline maternal characteristics, obstetric and neonatal will be obtained through medical records:

Maternal:	Neonatal:

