In general the evidence in aBME is limited. A few prospective studies has been conducted, and only one larger RCT. This RCT included 635 participants, where aBME was performed from week 36 of pregnancy. They were not able to detect any difference in gestational age at birth or report any adverse events in relation to the aBME. Before the larger RCT they conducted a pilot study, which consisted of 43 participants. Our aim with this study is to primarily test safety and feasibility with the procedure aBME from week 34, and since no study has been done from this week of pregnancy, a reliable power calculation is not possible to make. Therefore we estimated that 30 participants in each group is a realistic and feasible number to include in the pilot study. To detect a difference in gestational age at birth based on 80% power, we estimated that we would need a total of 176 participants, 88 in each group (mean, SD, derived from Soltani et al(19)). If the pilot study shows no trend towards a higher proportion of preterm birth in the intervention group, we will proceed to the larger trial.

Data collection:

Demographic data on the mothers (maternal age, education level, ethnic background, parity and smoking status) will be obtained through medical files. Infant data on gestational age, complications such as preterm contractions or birth and feedings from birth, will be obtained from medical records after birth. To obtain data on aBME and breastfeeding rates after birth, we will use SMS tracking via an app based in the RedCap system. From intervention start until 8 weeks after birth participants in the intervention group will receive a weekly sms, with questions on how many times they stimulated and if they were capable of expressing any milk. The control group will receive a weekly message which regards if they have been giving birth, to be able to initiate the questions on breastfeeding. After birth questions will regard breastfeeding initiation. After eight weeks the mothers experience and evaluation on the study will be evaluated in an online questionnaire.

Data analysis and statistics:

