### 2.2 Adherence to the intervention

We consider all participants who answer weekly questionnaires until 8 weeks post-partum as full completers. E.g. if participants try to follow the intervention as well as possible, but do not stimulate the breast the recommended fourteen times a week, we will still consider them as completers of the study, if they have stayed in the study during the intervention and until eight weeks after birth. However, we will differentiate between study completion and intervention completion. Intervention completion is defined as participants who follow the intervention as well as possible until birth but do not answer all eight questionnaires. These participants will be included in the analysis for gestational age at birth, but will only be included in the breastfeeding analysis as long as they have answered the weekly questions. If participants do not want to perform stimulation anymore, we consider this as a withdrawal of consent. If participants are not adherent to the randomized group, e.g. they start to stimulate antenatal even though they are in the control group, we consider them as excluded from the study.

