#### Antenatal breastmilk expression

- a)** Number of weekly expressions in the intervention group, measured through weekly push messages. Reported as median and IQR, and illustrated by a barplot figure over the number of weekly expression pr. women.
- b)** Amount of breastmilk expressed if any. How many women will be capable of expressing any milk before birth in the intervention group (counts and percentages), and how many mL (median and IQR). Volume is measured by each woman using a container with an mL scale and reported through weekly self-reported push messages. Milk volumes will be illustrated by a scatterplot over milliliter pr. week compared to the week of gestation.

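### The plan does not clearly provide for asking control women whether they expressed milk before birth, yet it excludes those who did; as written, contamination of the comparator would go unmeasured

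*Protocol*

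**What the plan says.** Only one text sets the content of the antenatal messages arm by arm, the protocol's Data collection section. For the intervention arm, "participants in the intervention group will receive a weekly sms, with questions on how many times they stimulated", together with a question on whether any milk came. For the other arm: "The control group will receive a weekly message which regards if they have been giving birth", the stated purpose being to start the feeding questions.

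Two other texts are less specific. The protocol's Intervention section says: "During the intervention and 8 weeks after birth the participating women will receive weekly push-messages through an application on their smartphone". It continues: "The messages include short questions about the aBME as well as regarding feeding of the infant after birth". SAP 4.1 lists weekly items on whether aBME was done, how often, and how much milk was collected, under a heading with no arm label. The block before it has a sub-list marked as intervention-only (the CTG items), and the later feeding items are marked as applying to both groups.

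On analysis, SAP 4.2.2 has "Number of weekly expressions in the intervention group, measured through weekly push messages". SAP 4.2.1 restricts adverse-event reporting to the intervention group. On non-adherent controls, SAP 2.2 says that if "they start to stimulate antenatal even though they are in the control group, we consider them as excluded from the study". SAP 3.4 has a withdrawal code for women unwilling to follow their allocation. Neither section names a question or time point that would identify such women.

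**The concern.** The value of the comparison depends on group B being largely unexposed. The trial is open label. Figure 1 in the protocol places randomisation at 28 to 32 weeks, before expression starts at 34+0. Controls are volunteers who plan to breastfeed exclusively and who have received written and oral information about the trial. Some could express on their own initiative, and the documents give no rate.

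The direction of the error matters here. The primary outcome is a safety outcome, SAP 4.2.1 plans a posterior probability of non-inferiority, and the protocol's Sample Size section makes progress to the larger trial depend on seeing no trend to more preterm births in the intervention arm. Exposure among controls moves all of these towards the favourable answer. If it is not recorded, a reader cannot tell a safe procedure from a diluted contrast. The pilot would also give no contamination estimate for planning the larger trial.

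**Working it through.** **Can controls be identified from the planned data?**

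- Data collection (protocol): the control message covers only whether birth has occurred. No aBME item.
- Intervention (protocol) and SAP 4.1: aBME items exist, arm not stated. If they were meant for both arms, they conflict with Data collection.
- SAP 4.2.1 and 4.2.2: adverse events and expression counts are for the intervention group only, so neither is a route to detection.
- 8-week questionnaire: its subject is the mother's experience; its content is not in the documents.
- SAP 2.2 and 3.4: a rule and a code for known cases, with no source of detection.

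**The plan's own figure.** The 176 women (88 per arm) for 80% power cannot be reproduced, because the mean difference and SD are not given. Solving backwards with a two-sided 5% level (sidedness is not stated) and the normal approximation:

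d = (1.960 + 0.842) × √(2/88) = 2.802 × 0.1508 = 0.422.

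A t-test gives 0.425, a rank-sum test with relative efficiency 0.955 gives 0.432, and a one-sided 5% level gives 0.375.

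**Dilution.** Let c be the share of controls who express. Assume that they are otherwise like the other controls, have the full intervention effect, and are analysed as randomised. The expected difference becomes d(1 − c), so:

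- power at 88 per arm = Φ(2.802 × (1 − c) − 1.960)
- number per arm to restore 80% = 88/(1 − c)², rounded up

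| c (assumed) | Expected controls exposed, of 30 | Power at 88 per arm | Per arm for 80% |
|---|---|---|---|
| 0 | 0 | 80% | 88 |
| 10% | 3 | Φ(0.562) = 71% | 109 |
| 20% | 6 | Φ(0.282) = 61% | 138 |
| 30% | 9 | Φ(0.001) = 50% | 180 |

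**The preterm-birth rule.** With preterm risk p₁ if exposed and p₀ if not, the control risk becomes (1 − c)p₀ + c·p₁, and the difference between arms becomes (1 − c)(p₁ − p₀). The trend on which progression depends shrinks by the same factor.

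**What asking would give.** If all 30 controls were asked and none reported aBME, the one-sided 95% upper bound on contamination would be 1 − 0.05^(1/30) = 9.5%. Without asking, there is no bound.

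**The case against.** A reader might infer that controls are never asked and that contamination cannot be detected. The documents do not establish this. The Intervention section and SAP 4.1 can be read as covering both arms, and the 8-week questionnaire, unfinished when the protocol was written, might include the question. What stands is narrower: the only arm-specific text gives controls no such item, the other texts are unclear, and the exclusion rule has no stated source of information.

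A reader might also infer that the sponsor expects controls to express. SAP 2.2 is conditional, and a contingency rule is not a forecast. The protocol gives aBME teaching, storage instructions, syringes and labels to the intervention group only, which works against contamination. It says "Participants will be recruited using video and text announcing on social media" but does not give the content of the announcement, so how much controls learn about aBME from it is unknown.

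The figures are open to challenge too. Both the contamination rates and the full effect in control expressers are assumed. The full effect is an upper-end choice, since controls would not be taught or scheduled for twice-daily sessions. The proportional shrinkage holds for means and proportions but need not hold for a difference in medians, which SAP 4.2.1 will report. The power loss belongs to a future trial, and no loss of planned power can be charged to the pilot, which has none.

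The most important objection concerns the remedy. With SAP 2.2 unchanged, a question put after birth would remove women from one arm only, once gestational age is known, in an open-label trial. That would replace dilution with selection. This objection stands, and the fix must deal with it.

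**Conclusion.** The point holds as a gap in data capture. The plan does not clearly provide for measuring antenatal expression in group B, while SAP 2.2 attaches a consequence to it. Taking Data collection as written, contamination would be unmeasured and would favour a finding of safety. Whether any occurred, and how much, cannot be known from the documents.

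The size is illustrative: power of the 88-per-arm trial falls from 80% to about 71%, 61% or 50% at assumed rates of 10%, 20% or 30%, given a back-solved d of about 0.42, a two-sided 5% level and full effect in control expressers. A weaker effect in those women would mean less loss. The change is worth making because it is cheap and because the protocol says that this pilot is meant to test safety and feasibility.

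**What to change.** 1. Reconcile the protocol's Intervention and Data collection sections with SAP 4.1, stating which arm receives each aBME item. Add one item to group B's first message after birth: did she express or stimulate her breasts before birth and, if so, from which week and about how often? Asking once, after birth, avoids prompting controls to start. Women who have already delivered can be asked in the 8-week questionnaire.
2. Report the number and percentage of controls exposed, out of those who answered, beside group A's expression counts. Interpret the gestational-age comparison in that light.
3. Amend SAP 2.2 so that the answer does not trigger exclusion from the analysis. Keep these women in group B for the intention-to-treat analysis named in the protocol's Data analysis and statistics section, because the answer arrives after the outcome is known.

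The cost is one REDCap item, short edits to both documents, and some recall error. For a birth at 40 weeks, recall back to week 34 is about 6 weeks at the first message after birth and about 6 + 8 = 14 weeks at the 8-week questionnaire. Frequency will be less reliable than the yes/no answer.
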